6.2 Statistical tests

If a statistical test is performed, the level of significance will be 0.05 (two-sided), unless stated otherwise.

There will be no multiplicity adjustment for the statistical tests.

6.3 Assessments, observations and tests: Permitted timing and handling in statistical analyses

In principle, data obtained at the time-points shown in the case report forms, and collected in accordance with the performance schedule shown in the study protocol, will be used for the statistical analysis. In the case of data reported at the discontinuation visit, the time-points for use in analyses will be determined on the basis of the permitted ranges in the performance schedule. If there is duplication by data obtained at the scheduled visits and data obtained at the discontinuation tests, the data obtained closest to the scheduled date will be used. If this does not eliminate duplication, data from the scheduled visit will be used. Unscheduled visits will not be included in the time-points for analysis. For the permitted ranges for the observation, test, and evaluation time-points shown in the study protocol, refer to Appendix 2.

For the final evaluation, data obtained at weeks 51 to 52 or at discontinuation of the treatment/tapering period will be used, except for CDRS-R and CGI-S scores, for which those obtained at week 50 or at discontinuation of the treatment period are used. However, if none of the above data are available, the latest data among reported data collected at scheduled visits are used for the final evaluation.

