5.2 Dosage and regimen

All subjects will receive oral duloxetine once daily after breakfast for 51 or 52 weeks (a 50-week treatment period and 1- to 2-week tapering period) from the day after registration (Visit 2). Note that, once or twice between Visits 5 and 17, the subjects should visit the study site without taking a dose to collect a blood sample for pre-dose PK (refer to Section 7.6). Table 5-1 shows the treatment regimens for the study drug. During the treatment period, the subjects will receive duloxetine 20 mg/day for one week then 40 mg/day for one week, and subsequently receive either 40 mg/day or 60 mg/day for 48 weeks as appropriate.

Subjects who complete the treatment period or who withdraw from it during Week 2 or later of treatment period will be transferred to the tapering period. During the tapering period, subjects whose duloxetine dose at discontinuation or completion of the treatment period is 60 mg/day will receive 40 mg/day for one week then 20 mg/day for one week. Subjects whose duloxetine dose at discontinuation or completion of the treatment period is 40 mg/day will receive 20 mg/day for one week. However, tapered administration may be omitted if serious adverse drug reactions occur, there are safety-related problems, or the subject or his/her legal representative refuses the tapered administration.

Table 5-1. Treatment Regimens

Treatment period			Tapering period	
Week 1	Week 2	Weeks 3 - 50	Week 51	Week 52
20 mg/day	40 mg/day	60 mg/day	40 mg/day	20 mg/day
1 x 20 mg LY248686 capsule	2 x 20 mg LY248686 capsule	3 x 20 mg LY248686 capsule	2 x 20 mg LY248686 capsule	1 x 20 mg LY248686 capsule
		40 mg/day	20 mg/day	-
		2 x 20 mg LY248686 capsule	1 x 20 mg LY248686 capsule	-

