7.7.5 Electrocardiogram

Standard, 12-lead electrocardiogram (ECG) will be performed at Visits 1 (or Visit 2 for consecutive subjects), 5, 11, and 18 (or at discontinuation of the tapering period; if not transferred to the tapering period, at completion or discontinuation [Visit 17] of the treatment period). For consecutive subjects, a measurement at Visit 9 in the preceding study may be used as a measurement at Visit 2 of this study. The principal investigator or sub-investigator will judge whether ECG results are normal or abnormal, and will record the date of ECG, the judgment, and any abnormal findings in the CRF.

If there are abnormal findings, the principal investigator or sub-investigator will judge whether the abnormal change from baseline (i.e., Visit 1 for new subjects or Visit 2 for consecutive subjects) is clinically significant (refer to Section 7.7.7.7), and will record any changes judged to be clinically significant as adverse events.

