7.7.6 Laboratory tests

7.7.6.1 Laboratory test items

At Visits 1 (or Visit 2 for consecutive subjects), 5, 8, 11, 14, and 18 (or at discontinuation of the tapering period; if not transferred to the tapering period, at completion or discontinuation [Visit 17] of the treatment period), blood samples will be collected for laboratory tests, the volumes being 2 mL for hematology tests, and 8 mL and 5 mL for blood chemistry tests, at Visit 1 and other visits, respectively; and urine samples will also be collected. The samples will then be sent to the clinical laboratory facility specified in Section 7.7.6.2. Details of the collection, handling, storage, and shipment of samples are stipulated in a separate document. For new subjects, blood samples and urine samples at Visit 1 will be collected after obtaining informed consent, between 3 weeks before the initial administration of the study drug and Visit 2. For consecutive subjects, a measurement at Visit 9 in the preceding study may be used as a measurement at Visit 2 of this study. Both new subjects and consecutive subjects will be registered after the latest measurements at Visit 2 are confirmed.

The principal investigator or sub-investigator will judge whether the abnormal change from baseline (i.e., Visit 1 for new subjects or Visit 2 for consecutive subjects) is clinically significant (refer to Section 7.7.7.7), and will record any changes judged to be clinically significant as adverse events. The sample collection dates will be recorded in the CRF for each sample type (blood or urine).

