10.2 Analyses of vital signs and body weight

Blood pressure (systolic and diastolic), pulse rate, and body weight will be analyzed. The time-points for evaluation of vital signs and body weight are taken to be the baseline, weeks 4, 16, 28, 40, and 50 after administration initiation, and the final evaluation time (weeks 51 to 52, or at discontinuation of the treatment period or tapering period).

- 1) With respect to blood pressure (systolic and diastolic), pulse rate, and body weight, summary statistics of observed values at each evaluation time-point and changes from baseline will be calculated.
- 2) For consecutive subjects, summary statistics of observed values at each evaluation time-point in the preceding study and this study and changes from baseline in the preceding study will be calculated.

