10.4 Analysis of ECG

The presence or absence of ECG abnormalities will be analyzed. The time-points for evaluation of ECG are taken to be baseline (Visit 1 for new subjects, Visit 2 for consecutive subjects), weeks 4 and 28 after administration initiation, and the final evaluation time (weeks 51-52, or at discontinuation of the tapering period).

- 1) With respect to the presence or absence of ECG abnormalities, the frequency of each category before and after administration initiation as well as before administration initiation and the final evaluation time (weeks 51-52, or at discontinuation of the treatment period or tapering period) will be summarized in the form of a shift table. With respect to categories after administration initiation, events will be taken to have occurred once, in the category with the highest of the below priority ranks.

Priority rank	Survey item category	
	Judgment	
1	Abnormal, clinically significant	
2	Abnormal, not clinically significant	
3	Normal	
4	Not observed	

- 2) With respect to the presence or absence of ECG abnormalities, the number and proportion of subjects in each category at each evaluation time-point will be determined.

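### The safety final evaluation is mainly a post-taper value pooled with untapered ones; it may understate reversible on-dose effects, and SAP 10.4 defines the final ECG in two ways

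*SAP*

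**What the plan says.** SAP 6.3 defines one final evaluation for every measure except the two efficacy scales: "For the final evaluation, data obtained at weeks 51 to 52 or at discontinuation of the treatment/tapering period will be used". The scales are handled differently: "except for CDRS-R and CGI-S scores, for which those obtained at week 50 or at discontinuation of the treatment period are used". There is also a fallback: "if none of the above data are available, the latest data among reported data collected at scheduled visits are used for the final evaluation".

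SAP 10.2 repeats the rule for blood pressure, pulse and weight: "the final evaluation time (weeks 51 to 52, or at discontinuation of the treatment period or tapering period"). It also lists weeks 4, 16, 28, 40 and 50 as separate time-points. SAP 10.3 lists weeks 4, 16, 28 and 40 for laboratory tests, and SAP 10.4 lists weeks 4 and 28 for ECG. In its list of time-points, 10.4 gives "the final evaluation time (weeks 51-52, or at discontinuation of the tapering period"). Its shift table also includes discontinuation of the treatment period.

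Under Protocol 5.2 a subject whose last treatment-period dose "is 60 mg/day will receive 40 mg/day for one week then 20 mg/day for one week"; a subject on 40 mg/day receives 20 mg/day for one week. The taper may be omitted for serious adverse drug reactions, other safety problems or refusal.

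Protocol 7.7.5 schedules post-baseline ECGs at Visits "5, 11, and 18 (or at discontinuation of the tapering period"), and Protocol 7.7.6.1 schedules laboratory tests at Visits "5, 8, 11, 14, and 18 (or at discontinuation of the tapering period"). In both, Visit 17 is used only when there is no taper. Protocol 7.7.3 and 7.7.4 measure weight, blood pressure and pulse at Visit 17 or treatment-period discontinuation, and again at Visit 18.

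**The concern.** Long-term safety is the primary objective. A reader of the tables will naturally take a row called final evaluation as the state after about a year on 40 or 60 mg/day. For most subjects it describes the end of a step-down to 20 mg/day, and for some it describes the dose at which they stopped. SAP 10.2 to 10.4 neither mark the row as post-taper nor separate the two kinds of value. If a change in blood pressure, pulse or a laboratory value depends on dose and reverses quickly, this row would show less of it than was present on treatment.

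Two further points concern subjects who stop early. Their on-dose vital signs may appear in no by-visit row. Read literally, the ECG time-point list also leaves out of its final row the discontinuation ECGs of early withdrawals without a taper, and serious adverse drug reactions are one stated reason for omitting the taper.

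**Working it through.** **The plan's own figure.** Protocol 8.2 and SAP 4.3 target 100 one-year subjects with 25% dropout: 100 / 0.75 = 133.3, so 134, against 135 stated. This agrees within rounding. Planned withdrawals are 135 × 0.25 = 33.75, about 34. Nothing below disputes that number.

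**What Visit 18 measures (Protocol Table 7-3, SAP Appendix 2).**
- From 40 mg/day: Day 7 ± 3 after Visit 17 or discontinuation, so 4 to 10 days after.
- From 60 mg/day: Day 14 ± 3, so 11 to 17 days after. The 20 mg/day step starts after 7 days, so this is 4 to 10 days after that step begins.
- The 20 mg/day step lasts one week, so a visit late in the window can fall up to 3 days after the last dose.

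**What else enters the row.**
- Early withdrawals with no taper contribute their treatment-period discontinuation value.
- Completers with no taper contribute Visit 17 through the fallback.
- An early withdrawal who tapers has two vital-sign values that both fit the SAP 6.3 definition: treatment-period discontinuation and Visit 18. The duplication rule in 6.3 concerns scheduled against discontinuation data for one time-point. It does not say which of these two is final.

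**Vital signs and weight by visit.** SAP 6.3 assigns discontinuation data by permitted range. The windows for the time-points in SAP 10.2 are:
- weeks 4, 16, 28 and 40: days 21–35, 105–119, 189–203 and 273–287, 15 days each;
- week 50: days 347–353, 7 days.

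Total: 4 × 15 + 7 = 67 of about 353 days (67 / 353 = 19%). A withdrawal at Day 140, for example, has a blood pressure that fits no listed row. It is tabulated only if it is chosen as final over Visit 18. The documents do not give the timing of withdrawals, so this cannot be turned into a number of subjects.

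**Laboratory tests and ECG in subjects who complete and taper.** The last scheduled on-dose laboratory test is week 40 (50 − 40 = 10 weeks before treatment ends). The last on-dose ECG is week 28 (50 − 28 = 22 weeks before).

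**Possible understatement, by assumption only.** Suppose an effect is proportional to dose and a share r of its dose-dependent difference has reversed by Visit 18. A tapered subject then shows 1 − r × (1 − 20/dose) of the on-dose effect:

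| r | from 40 mg/day | from 60 mg/day |
|---|---|---|
| 0 | 100% | 100% |
| 0.5 | 1 − 0.5 × 0.5 = 75% | 1 − 0.5 × 0.667 = 67% |
| 1 | 50% | 33% |

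Neither proportionality nor r is given in the documents. These figures show how far the answer depends on the assumption; they are not estimates.

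**The two ECG definitions in SAP 10.4.** The time-point list has weeks 51–52 or tapering-period discontinuation. The shift table and SAP 6.3 add treatment-period discontinuation. Protocol 7.7.5 does collect an ECG at treatment-period discontinuation when there is no taper, so the data exist but the time-point definition leaves them out of the final row.

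**The case against.** The different time-point for CDRS-R and CGI-S invites the inference that the SAP chose an on-dose endpoint for efficacy and a diluted one for safety. The documents do not support that. Neither scale is collected after Visit 17, so each final evaluation is simply the last planned assessment. Dosing is also defined as 51 or 52 weeks including the taper, and the row states its weeks openly.

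A reader might also infer that the long-term effect on blood pressure, pulse and weight is lost. It is not: SAP 10.2 summarises week 50 separately, and discontinuation values inside a listed window enter that visit's row.

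A third tempting step is to treat the 25% planned dropout as the untapered share and compute a pooled dilution. Under Protocol 3.1 and 5.2, subjects who withdraw in week 2 or later normally taper too, so that split has no basis. Nor are untapered values always at 40 or 60 mg/day: a subject who stops in week 1 is on 20 mg/day, and the discontinuation visit may fall up to 3 days after the last dose.

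The direction is not certain either. Weight may hardly move in one to two weeks, and discontinuation effects, which the taper is meant to limit, could move values the other way. Other analyses do not depend on this row: the worst-category ECG shift table, the any-time liver criteria, and adverse events for clinically significant changes.

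All of this stands, and it limits the claim. It does not answer the missing label, the mixed row, the unstated precedence, the unlisted discontinuation values or the two ECG definitions.

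**Conclusion.** The point holds in a limited form. For safety measures the SAP 6.3 final evaluation is mainly a post-taper value at 20 mg/day, pooled with untapered values. It may understate on-dose effects that reverse within one to two weeks. That it does so, or by how much, cannot be established: the documents give no dose-response, no reversal rate and no untapered share.

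Three parts rest on the text alone:
- On-dose vital signs and weight at discontinuation have no by-visit row outside windows covering 67 of about 353 days, and no stated precedence over Visit 18.
- Tapered subjects have no on-dose laboratory test scheduled after week 40 and no on-dose ECG after week 28. No SAP wording can supply those data.
- SAP 10.4 contradicts itself and SAP 6.3 on the final ECG. Untapered discontinuation ECGs are not lost altogether, because the shift table includes them, but the final row of the by-time-point table omits them.

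**What to change.** Change the SAP only; the visit schedule stays as it is.

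- **6.3 and 10.2:** add an end-of-treatment row for blood pressure, pulse and weight, defined as week 50 or treatment-period discontinuation. Report weeks 51 to 52 in a separate row labelled post-taper. This also settles which value counts when a subject has both.
- **10.3 and 10.4:** label weeks 51 to 52 as post-taper, tabulate values from subjects without a taper separately, and show the last on-dose value alongside. State as a limitation that tapered subjects have no planned end-of-treatment on-dose laboratory test or ECG.
- **10.4:** use the SAP 6.3 definition of the final evaluation throughout.

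The cost is SAP wording and a few table rows, with no new data. The drawback is smaller numbers in each row.

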7.7.4 Blood pressure and pulse rate

The blood pressure (systolic and diastolic) and pulse rate, at rest, will be measured at Visits 1 (new subjects only), 2, 5, 8, 11, 14, 17 (or at discontinuation of the treatment period) and Visit 18 (or at discontinuation of the tapering period). For consecutive subjects, a measurement at Visit 9 in the preceding study may be used as a measurement at Visit 2 of this study. The date and result of measurement will be recorded in the CRF. The principal investigator or sub-investigator will judge whether any abnormal change from baseline (Visit 2) is clinically significant (refer to Section 7.7.7.7) and will record any changes judged to be clinically significant as adverse events.

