5.1 FAS

This comprises all subjects to whom the study drug has been administered at least once, and with whom the CDRS-R total score has been determined at baseline and at least once after initiation of study drug administration.

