5.2 Safety-analysis set

This comprises all subjects to whom the study drug is administered at least once.

6. Issues with statistical analysis, and data handling

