10.5 Analysis of Columbia suicide severity rating scale

Columbia Suicide Severity Rating Scale (C-SSRS) will be analyzed. The time-points for evaluation of C-SSRS are taken to be the screening period and all scheduled visits during the treatment period, and the final evaluation time (weeks 51-52 or at discontinuation of the treatment period or tapering period).

- 1) The distribution of categories (yes, no) on the below evaluation scale will be summarized in the form of a shift table before and after administration initiation as well as before administration initiation and the final evaluation time (weeks 51-52, or at discontinuation of the treatment period or tapering period). For categories before administration initiation, subjects with at least one “yes” assessment at any one evaluation time-point in the screening period or before administration initiation will be classified as “yes”, and other subjects will be classified as “no”. For categories

after administration initiation, subjects with at least one “yes” assessment at any one evaluation time-point after administration initiation will be classified as “yes”, and other subjects will be classified as “no”. Both before and after administration initiation as well as the final evaluation time, subjects with missing observed values at all evaluation time-points will be classified as “non-assessed subjects”.

- 2) The number and proportion of subjects in each category at each evaluation time-point will be determined.

Columbia suicide severity rating scale	
Suicidal ideation	1. Wish to be dead 2. Non-specific Active suicidal thoughts.
Suicidal behavior	1. Actual attempt 2. Non-Suicidal Self-Injurious Behavior 3. Self-Injurious Behavior, intent unknown 4. Interrupted attempt 5. Aborted attempt 6. Preparatory Act or Behavior 7. Suicidal behavior 8. Completed suicide

- 3) For the following five questions about suicidal ideation, the distribution on the highest question number with at least one “yes” answer will be summarized in the form of a shift table of before versus after administration initiation.

Question No.	Questions
1	Wish to be dead
2	Non-specific Active suicidal thoughts.
3	Active suicidal ideation with any methods (not plans) but without intent to act
4	Active suicidal ideation with some intent to act, without specific plan
5	Active suicidal ideation with specific plan and intent

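### The SAP 6.3 fallback for the final evaluation is not limited to post-dose values, so an early dropout's pre-dose safety value can stand as the final one

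*SAP*

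**What the plan says.** SAP 6.3 sets the source of the final evaluation. For safety measures, "data obtained at weeks 51 to 52 or at discontinuation of the treatment/tapering period will be used". When nothing of that kind exists, "if none of the above data are available, the latest data among reported data collected at scheduled visits are used for the final evaluation". Neither this sentence nor SAP 6.4, which allows LOCF at the final evaluation, says that the value must come from after the first dose.

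The population for these tables is the safety-analysis set: "This comprises all subjects to whom the study drug is administered at least once". The FAS is stricter and covers only subjects "with whom the CDRS-R total score has been determined at baseline and at least once after initiation of study drug administration".

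On timing, Protocol 5.2 starts dosing on the day after Visit 2. SAP 10.2 evaluates vital signs and weight at "baseline, weeks 4, 16, 28, 40, and 50 after administration initiation", and Protocol 7.7.4 matches this: blood pressure and pulse "will be measured at Visits 1 (new subjects only), 2, 5, 8, 11, 14, 17". Laboratory tests and ECG are likewise first repeated at Visit 5 (Protocol 7.7.5 and 7.7.6.1).

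SAP 10.4 plans two ECG shift tables, showing "the frequency of each category before and after administration initiation as well as before administration initiation and the final evaluation time". For C-SSRS, SAP 10.5 says that "subjects with missing observed values at all evaluation time-points will be classified as" non-assessed, and applies this at the final evaluation too.

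**The concern.** Visits 1 and 2 are scheduled visits in the visit-window table (Protocol Table 7-3, SAP Appendix 2), so the fallback can reach them. For a treated subject with no post-dose measurement, the rule then works as baseline carried forward. The subject enters the final-evaluation summary as unchanged, when in fact nothing was observed on drug.

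Long-term safety is the primary objective. The distortion has a known direction, towards no change. The n shown at the final evaluation can exceed the number of subjects with any post-dose measurement of that parameter. In the efficacy analysis, the FAS definition protects the CDRS-R total score from this. The safety-analysis set has no such condition.

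**Working it through.** **1. The plan's own figure.** Protocol 8.2 and SAP 4.3 give 100 one-year subjects, 25% dropout and 135 registered. 100 / (1 − 0.25) = 133.3, rounded up to 134, so 135 is consistent. Planned dropouts: 0.25 × 135 = 33.75, about 34.

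**2. Where the fallback lands for a subject with no post-dose value.**

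| Measure | Latest pre-dose scheduled value | Baseline | First scheduled post-dose value |
|---|---|---|---|
| Blood pressure, pulse, weight | Visit 2 | Visit 2 | Visit 5 (Day 21 to 35) |
| Laboratory tests, ECG | Visit 1 (new) or Visit 2 (consecutive) | the same visit | Visit 5 (Day 21 to 35) |
| C-SSRS | Visit 2 | all pre-dose assessments pooled | Visit 3 (Day 4 to 10) |

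In the first two rows the carried value is the baseline itself, so the change is exactly 0 and the ECG final shift shows no movement. For consecutive subjects, the Visit 2 value may be the Visit 9 value of the preceding study.

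**3. How a subject gets there.**
- Protocol 4.5 asks for discontinuation tests only where feasible.
- Protocol 7.9 treats out-of-window data as missing, and the discontinuation window is +3 days.
- Laboratory tests and ECG are scheduled at treatment discontinuation only for subjects who do not enter tapering (Protocol 7.7.5 and 7.7.6.1). Someone who stops in week 2 or 3, enters tapering and is then lost has neither, even after attending the discontinuation visit.
- SAP 6.3 keeps unscheduled visits out of the analysis time-points.

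**4. The ECG tables compared.** In the before/after table, this subject has no post-dose category and is *Not observed*. In the before/final table, SAP 6.3 supplies the baseline category. The same subject is therefore unobserved in one table and unchanged in the other.

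**5. C-SSRS.** Exclusion criterion 12 requires a C-SSRS at Visit 2, so every eligible subject has a fallback value. Under SAP 6.3 the non-assessed class at the final evaluation could hardly ever be used, although SAP 10.5 provides it.

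**6. Size.** The documents give no early-dropout count. Assume a constant hazard reaching 25% at week 50 (Day 350). The proportion stopped by day d is 1 − 0.75^(d/350).
- d = 21: 1.71%, × 135 = 2.3 subjects.
- d = 35: 2.84%, × 135 = 3.8 subjects.
- For C-SSRS (d = 4 to 10): 0.33% to 0.82%, or 0.4 to 1.1 subjects.

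If k of these lack discontinuation data, each adds a zero. With all 135 contributing, the mean final change is multiplied by (135 − k)/135:

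| Scenario | k | Multiplier |
|---|---|---|
| All early stoppers have discontinuation data | 0 | 1.000 |
| Constant hazard, none has | 3 to 4 | 0.978 to 0.970 |
| 17 of 34 dropouts before week 4, half without data | 8.5 | 0.937 |
| 17 of 34 dropouts before week 4, all without data | 17 | 0.874 |

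The last two rows are deliberately pessimistic assumptions.

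**The case against.** The strongest reply is that the SAP does not intend this. SAP 6.4 does not impute in principle and names only LOCF. BOCF appears in the abbreviation list, but no analysis section available to us uses it. The SAP 10.5 provision for non-assessed subjects, as the more specific rule, suggests that pre-dose values were not meant to fill the final evaluation. That is a fair reading of intent, but it does not settle the text. SAP 6.3 is a selection rule with no post-dose condition, whereas the SAP states such a condition where it wants one, as in the FAS and in the liver criterion counted over post-dose time-points. A programmer following 6.3 literally would carry the baseline.

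Three further points stand and limit the concern:
- Discontinuation tests are requested, and vital signs and weight are scheduled both at treatment discontinuation and at Visit 18, so most early dropouts should have usable data.
- Clinically significant changes are recorded as adverse events, in tables that the fallback does not touch.
- The affected outputs are descriptive, with no test or decision attached.

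A reader might also infer more than the documents support:
- *That SAP 10.4 directly contradicts SAP 6.3.* The *Not observed* category is defined for the pooled post-initiation ECG result, while 6.3 governs only the final evaluation. The outcome is inconsistent between two tables, but the rules do not collide.
- *That C-SSRS subjects must show no shift.* The before category counts a yes at any pre-dose assessment, whereas the fallback is a single latest value. A new subject with yes at Visit 1 and no at Visit 2 would shift.
- *That the carried value is always untreated.* Consecutive subjects may already have taken duloxetine in the preceding study. The value is pre-dose only with respect to this study.
- *That early leavers mostly stop for poor tolerability.* No passage says so.

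**Conclusion.** The gap is real. As written, SAP 6.3 can report a pre-dose value as the final evaluation of laboratory tests, vital signs, weight or ECG, and neither SAP 6.4 nor SAP 10.2 to 10.4 prevents it. For C-SSRS, SAP 6.3 and 10.5 need reconciling, though few subjects are exposed because the scale is repeated from Visit 3.

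The expected effect is small: a dilution of 0% to about 3% in the mean final change under constant hazard. About 6% to 13% would need half of all dropouts before week 4 and half to all of those without discontinuation data. A reader might assume a figure such as 3 to 10 affected subjects, but that would need a front-loaded pattern together with widespread failure of discontinuation testing, and the documents support neither.

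The effect is confined to final-evaluation summaries and shift tables, including the liver and ECG category proportions at that time-point. Adverse-event tables, by-visit summaries and the liver criteria counted over any post-dose time-point are unaffected. The point is still worth correcting: the primary objective is safety, the direction is known, and ECG categories may rest on small counts.

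**What to change.** In SAP 6.3, limit the fallback to scheduled-visit data obtained after the first dose in this study, and state that the final evaluation is missing when there are none. Then carry this through:
- SAP 10.2 and 10.3: leave such subjects out of n at the final evaluation.
- SAP 10.4: show them as *Not observed* in the before/final shift table.
- SAP 10.5: show them as non-assessed at the final evaluation, which restores the use of that class.

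This needs one sentence in 6.3 with matching notes in section 10, no new data and no change to the target of 135. The cost is a slightly smaller n at the final evaluation.
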